12.3 Statistical methods

All statistical analysis will be performed using SAS 9.2 (SAS, Cary, NY, USA) or newer.

In general, continuous variables will be described statistically using the number of cases, mean, median, standard deviation, minimum, and maximum; normally distributed data will be expressed as the mean \pm standard deviation, and skewed distribution data will be expressed as quartiles.

The categorical and grade variables will be described statistically using the frequency and percentage of each category or grade.

12.3.1 Case group analysis

(1) List the number of enrolled and completed clinical trial cases in each group will be listed, and the number and percentage of subjects in the three analytical data sets (SS, FAS, PPS) will be summarized;

(2) The number and proportion of subjects in each group who had early termination of trials for different reason will be summarized. The cases of shedding and removal, and their causes will be listed.

12.3.2 Demographic data and baseline analysis

Descriptive statistical demographic data and baseline characteristics:

(1) For the consecutive variables such as age, weight, vital signs, and the number of case, the mean, standard deviation, median, minimum, and maximum will be calculated.

(2) The count and grade data, such as gender, physical examination, will be used to calculate the frequency and composition ratio.

12.3.3 Safety Analysis

(1) AEs will be encoded according to MedDRA (International Medical Dictionary). The analysis of an AE will be based on the AE that occurs after UC-MSC treatment (TEAE). TEAE

is defined as an AE that occurs or worsens after UC-MSC treatment. For a TEAE in the treatment group, the TEAE may be related to UC-MSC treatment. An SAE will be analyzed according to the classification of system organs and preferred terms, and the number of occurrences and incidence rate will be calculated;

(2) Descriptive statistics will be used to summarize vital signs and laboratory tests. A shift table will be used to describe changes in normal/abnormal results in the laboratory tests before and after UC-MSC administration. In addition, the number and proportion of subjects will be calculated whose laboratory test are normal before treatment, but abnormal after treatment, or whose laboratory test are abnormal before treatment, but aggravated after treatment.

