If the researchers considered that abnormal laboratory tests (such as clinical biochemistry, hematology, urine analysis) were clinically significant, or other abnormal indicators (such as electrocardiogram, vital signs, or physical examination.) were clinically significant and met the definition of an AE or SAE, it would be recorded as an AE or SAE as well as being described by the symptoms and signs of the subjects. It should be regarded as AE or SAE if the clinically significant laboratory abnormalities and other abnormalities were found after the use of UC-MSC, or at the time of baseline assessment and are aggravated after the beginning of the study. However, the results of clinically significant abnormal laboratory tests or other abnormalities associated with the diseases would not be regarded as AE or SAE unless the researchers determined that the condition of the subject became more serious than expected or required medical treatment (such as withdrawal from this clinical trial or medical intervention). If laboratory findings or other anomalies that were present or found at the beginning of the study

are not aggravated, these events would be not included in AE and SAE.

Researchers will determine the clinical significance of an abnormal laboratory examination or other abnormalities according to the US national cancer institute standard and the actual situation of the subjects. All abnormal laboratory test results will be listed by the data statistician after the trail; meanwhile, the severity of those results is evaluated according to the NCI standard.

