9.5 AE and SAE assessment

9.5.1 Severity determination of an AE

Researchers should assess the severity of each reported AE and SAE based on their clinical knowledge and professional guidelines. The AE recorded in CRF should be classified according to the NCI-CTC AE 4.0 standard (see Appendix 4 for common AE grading standards):

Grade 1. Mild: Patients are asymptomatic or present mild signs; only clinical or diagnosis observation results are obtained; there is no need for interventional therapy;

Grade 2. Moderate: Patients need minimum, local, or non-invasive treatment; the ability of their instrumental daily life activities * is limited;

Grade 3. Serious or clinically significant, but not immediately life-threatening; hospitalization or prolonged hospitalization; disability; limited ability to take care of oneself via daily activities **

Grade 4: The abnormality leads to life-threatening consequences; the need for urgent intervention by clinical therapy;

Grade 5: An AE leads to death.

Illustration: The semicolon used in grade description mentioned above means "or";

A single dash means that this Grade does not exist;

Not all AE contain all levels. Thus, some AEs have less than five Grades to choose from;

Grade 5 (death) does not apply to some AEs, so there is no such level;

Activities of daily living (ADL);

*Instrumental daily life activities include, for example, cooking, shopping, using the telephone, and money management.

** Personal daily activities include, for example, bathing, undressing, eating, washing, taking medicine, and the patients is not bedridden.

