12.3.4 Efficacy analysis

The efficacy analysis will be based on the FAS set. PPS analysis will serve as an ancillary analysis for FAS. If the PPS results are inconsistent with the FAS results, it will be necessary to analyze and discuss the possible causes.

(1) Primary efficacy

All eligible participants who receive the assigned treatment and are followed up will be included in the analysis. We will count the number of endpoint events (death or HCC events) that occurred during the follow-up period and will compare the event-free time between the two groups using Kaplan–Meier analysis. The post-treatment follow-up will be continued until the date of an endpoint event, death, or the end of the study, whichever occurs first. Cox proportional-hazards models will be developed to estimate the hazard ratio (HR) and 95% confidence interval (CI) for between-group comparisons, with or without adjustments for stratification baseline MELD scores. Additionally, we will perform landmark analyses to assess the endpoint events accordingly, with the hazard ratio calculated separately for events that occurred before or after the landmark points.

(2) Secondary efficacy indicators

Liver function: The serum levels of ALB, PTA, CHE, and TBIL will be monitored within 48 weeks after the first UC-MSC infusion or routine medical treatment. A paired t-test will be applied to analyze the levels of ALB, PTA, CHE, and TBIL of the participants in each group post-treatment compared with those at baseline. The levels of ALB, PTA, CHE, and TBIL of the participants will also be compared between the treatment group and the control group at each specific evaluation timepoint. Student's t test or a non-parametric test will be applied when relevant.

Complications: MedDRA will be used to code and classify complications. For all cases, the

episode and severity of the complication will be listed by groups. The incidence by each study group and severity, respectively, will be calculated. The incidence between groups will be compared using the Chi-squared test or Fisher's exact test. Multiple Chi-squared comparisons will be performed on the basis of a Bonferoni-adjusted α value when relevant.

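### The normal/abnormal shift table and the count of 'aggravated' results in section 12.3.3 are weak summaries of laboratory safety for liver and coagulation tests; the NCI grades already required by section 9.3 should be used instead (minor)

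*Protocol*

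**What the plan says.** Section 12.3.3(2) of the protocol plans three summaries of laboratory safety.

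- General: "Descriptive statistics will be used to summarize vital signs and laboratory tests". Section 12.3 lists these for continuous variables as the number of cases, mean, median, standard deviation, minimum and maximum.
- Shift table: "A shift table will be used to describe changes in normal/abnormal results in the laboratory tests before and after UC-MSC administration".
- Count: the number and proportion of patients whose test goes from normal to abnormal, or is "abnormal before treatment, but aggravated after treatment". The section gives no size, grade or visit rule for the second part.

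Other sections also bear on laboratory results.

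- Section 9.3: "All abnormal laboratory test results will be listed by the data statistician after the trail", and at the same time "the severity of those results is evaluated according to the NCI standard". Abnormalities judged clinically significant, including baseline ones that get worse, become adverse events. Abnormalities associated with the disease are exempt unless they are more serious than expected or need medical treatment.
- Section 9.5.1: "The AE recorded in CRF should be classified according to the NCI-CTC AE 4.0 standard".
- Section 12.3.4, under efficacy: "The levels of ALB, PTA, CHE, and TBIL of the participants will also be compared between the treatment group and the control group".

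Section 12.3.3 does not use the severity grades of section 9.3 in the shift table or in the meaning of 'aggravated'.

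**The concern.** The shift table and the count are the only two summaries in section 12.3.3(2) that classify each patient's change from baseline. Both work poorly for a test that is already abnormal at entry.

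The table has two states. A patient who starts abnormal can only stay abnormal or become normal, so the table looks the same whether the value is stable or far worse. The count does admit worsening. Without a size rule, though, it may collect ordinary visit-to-visit variation along with real deterioration.

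Safety is the trial's secondary objective. In this population, deterioration of liver or coagulation tests is the signal these tables would be read for. A harmful effect in a minority of treated patients would be invisible in the first summary and hard to separate from background in the second.

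**Working it through.** The protocol gives no figure for laboratory safety, so there is nothing to reproduce. The check has two parts.

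**Inputs from the protocol**

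- Population: decompensated HBV cirrhosis (section 4.1). Raised ALT and AST are admitted below 10 times the upper limit of normal (section 4.2, criterion 7).
- Post-baseline biochemistry and coagulation draws: weeks 2, 4, 8, 12, 24 and 48, so k = 6 (sections 6.4 to 6.9).

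**Assumptions, not in the protocol**

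- The share q of patients abnormal at entry on a given test is 30% to 90%.
- Values are normal, on a scale where higher is worse, with total variance 1 and exchangeable within-patient correlation ρ of 0.5 to 0.9.
- There is no toxicity and no trend.
- 'Aggravated' means any value worse than baseline at any draw. The protocol does not say this. It is the widest reading the text allows.

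**Part 1: the two-state table.** Only patients normal at entry can move towards abnormal, a share of 1 − q. With q = 70% this is 30% of patients; with q = 90% it is 10%. For the rest, worsening has no cell.

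**Part 2: the count, under no toxicity.** For an unselected patient, the baseline is equally likely to be the worst of the k + 1 values. So P(at least one later value is worse) = k/(k + 1) = 6/7 = 86%.

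The 'aggravated' part of the count applies only to patients selected for an abnormal baseline, and their later values regress towards the mean. Write b for the baseline, s for the patient's own mean and c for the abnormality cut-off, with P(b > c) = q. Then

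P(flagged | abnormal at entry) = 1 − E[ Φ((b − s)/√(1 − ρ))^k | b > c ],

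where s given b is normal with mean ρb and variance ρ(1 − ρ). With k = 6:

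| ρ | q = 30% | q = 50% | q = 70% | q = 90% |
|---|---|---|---|---|
| 0.5 | 67% | 75% | 80% | 84% |
| 0.7 | 72% | 77% | 81% | 84% |
| 0.9 | 78% | 81% | 83% | 85% |

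Numerical integration and a simulation of 400,000 patients agree to within 0.3 percentage points. The range over the grid is 67% to 85%. With one post-baseline value (k = 1) it is 26% to 48%; with three (k = 3) it is 51% to 74%.

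The size of the chance count therefore depends strongly on which visits are used. It is substantial even when only one visit is used.

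**The case against.** The best case for the plan is that these two summaries do not stand alone, and most of that case is right.

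- The same section plans descriptive statistics of the laboratory values. A shift affecting most treated patients would show in the means, and an extreme value in the minimum or maximum.
- Section 9.3 lists every abnormal result and has its severity graded. Clinically significant deterioration becomes an adverse event, graded under section 9.5.1 and summarised under section 12.3.3(1).
- Section 12.3.4 compares ALB, PTA, CHE and TBIL between arms as continuous values.
- Visit selection and a numerical meaning for 'aggravated' are often left to a statistical analysis plan, which is not at hand.

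Some limits remain. Means can miss a severe change in a few patients. A listing gives no rate by arm. The adverse-event route depends on investigator judgement in an open-label trial and exempts much disease-related abnormality. The comparison in section 12.3.4 does not name ALT, AST or creatinine, and section 7.2 sets its assessments at weeks 12, 24 and 48, so it does not clearly cover weeks 2 to 8. The two-state format is also not an omitted detail: the protocol itself fixes it, while requiring finer grades elsewhere.

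A reader might infer three stronger things that the documents do not support.

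- *That laboratory safety as a whole is close to uninformative.* The other summaries above contradict this.
- *That renal or haematological toxicity would be hidden.* Section 4.2 excludes creatinine clearance below 50 mL/min and serious blood disease, including various anaemias. Much of that panel may be normal at entry, where a normal/abnormal table works.
- *That 86% of patients abnormal at entry are flagged by chance, whatever the correlation.* The 6/7 result is for unselected patients. Once they are selected on an abnormal baseline, the figure is lower and depends on both ρ and q.

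Nor is a power comparison of different counts informative here. No hypothesis test of laboratory safety is specified, and any threshold in standard-deviation units would be invented.

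**Conclusion.** The point holds for the shift table and the 'aggravated' count, mainly for liver and coagulation tests, and it is minor. The blindness of the two-state table to worsening in patients abnormal at entry follows from its form. How many patients this affects is an assumption, because the protocol gives no baseline proportions. The 67% to 85% chance rate applies only to the any-visit, any-size reading of 'aggravated', within the stated ranges for q and ρ. A narrower reading lowers it, but the text does not choose one.

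One related matter affects how these tables can be read. Section 12.2 defines the safety set by receipt of at least one UC-MSC infusion. As worded, it contains no control patients, so there would be no background rate against which to judge either summary.

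**What to change.** In section 12.3.3(2):

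1. Replace the normal/abnormal shift table with a table of NCI-CTC AE v4.0 grade at baseline by worst post-baseline grade to week 48, for each test.
2. Define 'aggravated' as a rise of at least one grade from baseline. For tests the standard does not grade, prespecify a change from baseline.
3. Show the tables for both arms, and state expressly that control patients are included despite the infusion requirement in the safety set of section 12.2.
4. Keep the descriptive statistics and the listing. They show changes within a grade, which a grade table does not.

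The cost is slightly more tabulation and a wording change. No extra visits or samples are needed, and section 9.3 already requires the severity of abnormal results to be graded.

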12.3.4 Efficacy analysis

The efficacy analysis will be based on the FAS set. PPS analysis will serve as an ancillary analysis for FAS. If the PPS results are inconsistent with the FAS results, it will be necessary to analyze and discuss the possible causes.

(1) Primary efficacy

All eligible participants who receive the assigned treatment and are followed up will be included in the analysis. We will count the number of endpoint events (death or HCC events) that occurred during the follow-up period and will compare the event-free time between the two groups using Kaplan–Meier analysis. The post-treatment follow-up will be continued until the date of an endpoint event, death, or the end of the study, whichever occurs first. Cox proportional-hazards models will be developed to estimate the hazard ratio (HR) and 95% confidence interval (CI) for between-group comparisons, with or without adjustments for stratification baseline MELD scores. Additionally, we will perform landmark analyses to assess the endpoint events accordingly, with the hazard ratio calculated separately for events that occurred before or after the landmark points.

(2) Secondary efficacy indicators

Liver function: The serum levels of ALB, PTA, CHE, and TBIL will be monitored within 48 weeks after the first UC-MSC infusion or routine medical treatment. A paired t-test will be applied to analyze the levels of ALB, PTA, CHE, and TBIL of the participants in each group post-treatment compared with those at baseline. The levels of ALB, PTA, CHE, and TBIL of the participants will also be compared between the treatment group and the control group at each specific evaluation timepoint. Student's t test or a non-parametric test will be applied when relevant.

Complications: MedDRA will be used to code and classify complications. For all cases, the

episode and severity of the complication will be listed by groups. The incidence by each study group and severity, respectively, will be calculated. The incidence between groups will be compared using the Chi-squared test or Fisher's exact test. Multiple Chi-squared comparisons will be performed on the basis of a Bonferoni-adjusted α value when relevant.

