3.2 Endpoints

3.2.1 Primary endpoints

(1) Survival rate during 75 months posttreatment follow up.

(2) Hepatocellular carcinoma (HCC)-free survival rate during 75 months of posttreatment follow up.

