7.1 Survival analysis

The patients will be followed up for 75 months to record their survival status and survival rate after their first UC-MSC infusion. During the follow-up period, the survival rate of those patients is dependent on the survival status at the last visit point after the first infusion. The time of death of those patients will be recorded and the survival rate will be calculated.

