8.2 Concomitant treatments

Except for infusion of UC-MSC, all other treatments given to subjects at the time of entry into the trial or at any time during the trial will be considered concomitant treatment and the drugs used should be recorded in the CRF under their generic names. The concomitant drugs must be necessary for the subjects to use during the trial. The use of concomitant drugs could be allowed if the researchers consider that those drugs have no influence on UC-MSC efficacy. Meanwhile, the dose of the concomitant drugs should be kept to a minimum.

9 Safety evaluation

It is the responsibility of the researchers to identify and record events that meet the definitions of adverse events (AEs) and serious adverse events (SAEs) specified in this study.

Long-term safety is a major concern for this trial. Hepatocellular carcinoma (HCC) occurrence is defined as the long-term adverse events in this clinical trial. The duration between the first infusion and timepoint of HCC occurrence will be recorded during 75 months of follow-up. This duration will be defined as survival rate of patients without HCC.

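### Sections 7.1, 9 and 12.3.4 of the protocol give conflicting event and follow-up rules for the two primary endpoints, overall survival and HCC-free survival

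*Protocol*

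**What the plan says.** Section 3.2.1 of the protocol names two primary endpoints, "Survival rate during 75 months posttreatment follow up" and "Hepatocellular carcinoma (HCC)-free survival rate during 75 months of posttreatment follow up", without defining the event for either. Three later sections supply rules.

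- **Section 7.1** covers survival: "The patients will be followed up for 75 months to record their survival status and survival rate after their first UC-MSC infusion", and "The time of death of those patients will be recorded and the survival rate will be calculated". It makes no exception after HCC. Sections 6.10 to 6.13 schedule telephone calls at months 24, 48, 60 and 75 that ask about survival status and liver cancer, again with no exemption.
- **Section 9** (opening text) covers HCC: "The duration between the first infusion and timepoint of HCC occurrence will be recorded during 75 months of follow-up", followed by "This duration will be defined as survival rate of patients without HCC". Death is not mentioned.
- **Section 12.3.4, Primary efficacy**, covers the analysis: "We will count the number of endpoint events (death or HCC events) that occurred during the follow-up period". It then gives one rule for the end of follow-up: "The post-treatment follow-up will be continued until the date of an endpoint event, death, or the end of the study, whichever occurs first". It does not say which event belongs to which endpoint.

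**The concern.** Overall survival and HCC-free survival have different events, so one event list with one stopping rule cannot serve both. The analyst has to choose a reading, and each reading damages one of the primary endpoints.

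If HCC is an endpoint event for everyone, follow-up stops at HCC and the deaths that come after it never reach the overall survival analysis. Patients who develop HCC have a worse prognosis than those who do not, so censoring them there is informative. If HCC is an event only for the second endpoint, that endpoint is time to HCC with death censored. In decompensated cirrhosis death is a frequent competing event and the one that the treatment is meant to reduce. A Kaplan–Meier curve built that way is not a survival rate and reads well above the proportion alive and free of HCC.

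The trial is open label (section 3.3), so this choice should not remain open once outcomes by arm can be seen.

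**Working it through.** **1. The rules side by side**

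| Source | Event for overall survival | Event for HCC-free survival | Does HCC end follow-up? |
|---|---|---|---|
| 7.1 and 6.10–6.13 | death | not addressed | no |
| 9 | not addressed | HCC only | not addressed |
| 12.3.4, literal reading | death, seen only up to HCC | death or HCC | yes |
| 12.3.4, endpoint-by-endpoint reading | death | HCC, with death ending follow-up | not for overall survival |

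The literal reading of 12.3.4 contradicts 7.1 on follow-up and section 9 on the event. The endpoint-by-endpoint reading agrees with both, but leaves a primary endpoint named as a survival rate that does not count death.

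**2. The plan's own figure**

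Section 12.1 claims more than 80% power with 100 per group. The sentence is garbled; its most plausible meaning is 60% against 85% disease-free at 60 months. Then HR = ln(0.85)/ln(0.60) = 0.318. With 40 months of accrual and 75 months in total, about 51 events are expected, and power is 96% (Freedman) to 98% (Schoenfeld). The claim of more than 80% is therefore true. It does not settle this point, because section 12.1 does not define disease-free survival and the term is not one of the named endpoints.

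**3. Illustration of the literal rule, control arm, fixed 75 months**

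Assumptions not in the document: the 60% is freedom from death or HCC, hazards are constant, a share q = 25–50% of first events is HCC, and median survival after HCC is 12–24 months.

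- Composite hazard: λ = −ln(0.60)/60 = 0.00851 per month.
- First events by month 75: F = 1 − exp(−75λ) = 0.472, so 52.8% are alive and free of HCC.
- Deaths without HCC: (1 − q)F.
- Deaths after HCC, with m = ln 2/median: k = qF − qλ[exp(−75λ) − exp(−75m)]/(m − λ).
- True overall survival: 1 − (1 − q)F − k.
- Overall survival as read if patients are censored at HCC: exp(−(1 − q)75λ).

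| q | Median after HCC (months) | Deaths without HCC | Deaths after HCC | Share of deaths after HCC | True overall survival | As read | Difference (points) |
|---|---|---|---|---|---|---|---|
| 25% | 12 | 35.4% | 9.6% | 21% | 55.0% | 61.9% | 6.9 |
| 25% | 24 | 35.4% | 7.5% | 17% | 57.1% | 61.9% | 4.8 |
| 33% | 12 | 31.5% | 12.8% | 29% | 55.8% | 65.3% | 9.6 |
| 33% | 24 | 31.5% | 10.0% | 24% | 58.6% | 65.3% | 6.8 |
| 50% | 12 | 23.6% | 19.1% | 45% | 57.3% | 72.7% | 15.4 |
| 50% | 24 | 23.6% | 15.0% | 39% | 61.5% | 72.7% | 11.2 |

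Censoring at HCC is one way to apply the literal rule. If HCC were instead counted as an event in the overall survival analysis, the curve would read 52.8%, which is 2 to 9 points below the true values in the table.

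**4. Illustration of the HCC-only reading**

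Under the same assumptions, the HCC-only Kaplan–Meier estimate at month 75 is exp(−q·75λ): 85% for q = 25% and 73% for q = 50%. The proportion alive and free of HCC is 53%.

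**The case against.** The strongest reply is that the protocol does collect the deaths. Section 7.1 follows survival for 75 months and records time of death, the calls at months 24 to 75 exempt nobody with HCC, and section 10.1 defines completion as all visits through visit 8. The stopping sentence also lists death separately from an endpoint event. That would be redundant if an endpoint event already meant death or HCC for both endpoints, so an endpoint-by-endpoint reading is natural. Nor does 12.3.4 expressly make HCC-free survival a composite.

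All of this stands. A reader might infer that deaths after HCC will certainly be missing from overall survival; the documents do not support that. They show a conflict between 12.3.4 and 7.1, and the loss follows only from the literal reading. The reply does not remove the problem, though: the reading that protects overall survival is the one that leaves death censored in HCC-free survival.

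A reader might also infer that an HCC harm would be hidden. Take a chosen scenario: 125 per arm, fixed 75 months, HCC one third of control first events, median 12 months after HCC, UC-MSC doubling HCC and cutting other deaths by 30%. True overall survival is about neutral (mean log-rank z +0.2, negative favouring UC-MSC). Censoring at HCC shifts it to −1.4, with significant benefit in about 29% of runs. But the death-or-HCC comparison that 12.3.4 names gives about +0.7 in the same scenario, with significant benefit in about 0.5% of runs. The excess HCC would therefore not be hidden overall.

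Finally, a reader might conclude that HCC-only events leave the trial underpowered. That presumes that the undefined disease-free survival of section 12.1 means death or HCC, which the protocol does not say.

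**Conclusion.** The event and follow-up rules for the primary endpoints conflict as written. This is more than detail left to an analysis plan, because the protocol states the rules and they cannot all be followed. The literal reading cuts overall survival at HCC, against 7.1 and the scheduled calls. The endpoint-by-endpoint reading leaves overall survival intact but censors death in HCC-free survival.

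The sizes are illustrative: about 17–45% of deaths by month 75 occurring after HCC, and 75-month overall survival overstated by about 5–15 points. They hold only under the literal rule with censoring at HCC, and they rest on an assumed HCC share, an assumed survival after HCC, constant hazards and one reading of section 12.1. That the rules conflict depends on none of these.

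Time zero is a minor matter. Sections 7.1 and 9 count from a first infusion that controls never receive, but section 6 labels week 0 as baseline and screening lasts at most 7 days, so any shift is small against 75 months.

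**What to change.** In section 12.3.4, replace the pooled event list and the single stopping rule with one rule per endpoint:

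- **Overall survival:** the event is death from any cause. HCC is neither an event nor a censoring point, and survival status is collected to month 75.
- **HCC-free survival:** the event is the first of HCC or death from any cause.

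Correct the section 9 sentence to match. Time to HCC can remain as a safety outcome, reported by arm with death treated as a competing event; the choice of estimator can be left to the analysis plan. Reconcile section 7.1 with the same definitions, and use one time zero, randomisation or week 0, in both arms.

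The cost is protocol wording and a confirmation that the calls at months 24, 48, 60 and 75 continue after an HCC diagnosis. No visit or measurement is added, since those calls already ask about survival status and HCC.

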3.2.2 Secondary endpoints

(1) Liver function, including the levels of albumin (ALB), prothrombin activity (PTA), total bilirubin (TBIL), and cholinesterase (CHE) during 48 weeks after the first UC-MSC infusion..

(2) Complications, including abdominal infection, gastrointestinal hemorrhage, hepatic encephalopathy, and hepatorenal syndrome during 48 weeks after the first UC-MSC infusion.

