7.2 Secondary Efficacy Assessments

Liver function (including the levels of albumin [ALB], prothrombin activity [PTA], total bilirubin [TBIL], and CHE) will be evaluated at 12, 24, and 48 weeks after the first UC-MSC

infusion.

The complications assessment will be followed-up for 48 weeks post-treatment (including infection, gastrointestinal bleeding, encephalopathy, and hepatorenal syndrome).

The diagnosis of complications

The diagnosis of ascites and hepatorenal syndrome will be made according to the AASLD ascites guidelines for liver cirrhosis (2004).

The diagnosis and treatment of hemorrhage and cirrhotic variceal bleeding will be made according to the AASLD guidelines for liver cirrhosis (2008).

The diagnosis of hepatic encephalopathy will be made according to guidelines of the 11th World Congress of Gastroenterology (WCOG), a working group that was established to discuss and summarize hepatic encephalopathy, and "The definition, nomenclature, diagnosis and quantitative analysis of hepatic encephalopathy" was published in the journal of the American society of hepatology in 2002.

8 Concomitant Diseases and Treatments

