12.4 Statistical software and general requirements

(1) Analysis will be performed using SAS 9.2 or newer;

(2) The estimated overall survival rate and HCC-free survival rate, as well as bilateral 95% confidence intervals, will be calculated;

(3) Unless there is another declaration, the hypothesis testing will be two-sided with an α value of 0.05.

13 Clinical trial management

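### Liver function is tested within each arm and by unadjusted between-arm tests; adjusting for the baseline already collected, with one key visit and a multiplicity rule, would be better at almost no cost

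*Protocol*

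**What the plan says.** Protocol section 3.2.2 lists the first secondary endpoint as "Liver function, including the levels of albumin (ALB), prothrombin activity (PTA), total bilirubin (TBIL), and cholinesterase (CHE) during 48 weeks". It ranks no marker and no visit above the others. Section 7.2 says that these markers "will be evaluated at 12, 24, and 48 weeks after the first UC-MSC" infusion.

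Section 12.3.4, part (2), fixes two analyses:
- **Within each arm:** "A paired t-test will be applied to analyze the levels of ALB, PTA, CHE, and TBIL of the participants in each group post-treatment", compared with baseline.
- **Between arms:** the levels "will also be compared between the treatment group and the control group at each specific evaluation timepoint", where "Student's t test or a non-parametric test will be applied when relevant".

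For these markers it names no baseline covariate, no between-arm comparison of changes, no repeated-measures model and no arm difference with a confidence interval.

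On error control, section 12.4 states "Unless there is another declaration, the hypothesis testing will be two-sided with an α value of 0.05". The only other declaration on secondary endpoints closes the complications paragraph of 12.3.4: "Multiple Chi-squared comparisons will be performed on the basis of a Bonferoni-adjusted α value when relevant".

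**The concern.** A paired test in one arm asks whether that arm changed, not whether the cells changed it. Both arms receive conventional treatment, so any movement common to both appears in each paired test. If the two arms' paired p-values are then read side by side, a result that is significant in one arm only can look like a treatment effect when there is none.

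The between-arm tests do address the treatment question, but with less information than the trial collects. The visit schedule has biochemistry and coagulation at screening, so a pre-treatment value of all four markers exists for each patient. Comparing follow-up levels alone leaves the part of the outcome variance that baseline explains in the error term, and leaves any chance baseline difference in the estimate.

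With no key marker or visit and no adjustment, a report could also feature whichever of several comparisons falls below 0.05.

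**Working it through.** The protocol gives no effect size, SD, correlation or power for liver function. Its power statement (section 12.1) concerns the primary endpoint, so there is no figure of its own to reproduce here.

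**1. Number of tests.** Inputs: 4 markers (3.2.2), 3 evaluation weeks (7.2), 2 arms.
- Between arms: 4 × 3 = 12.
- Within arms: 4 × 3 × 2 = 24.
- Total: 36, each at two-sided 0.05 by the default in 12.4. The Bonferroni sentence concerns Chi-squared comparisons of complications and does not reach them.

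**2. Chance of at least one false positive among the 12 between-arm tests when there is no effect.**
- Independent tests: 1 − 0.95^12 = 0.460. Expected false positives: 12 × 0.05 = 0.6.
- Correlated tests, by simulation (100 per arm, 4,000 trials per setting, simulation error about 0.8 percentage points). Both correlations are assumed:

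| Between-marker r | Between-visit r = 0.5 | Between-visit r = 0.7 |
|---|---|---|
| 0 | 41.4% | 37.8% |
| 0.3 | 38.8% | 34.9% |
| 0.5 | 36.3% | 31.8% |

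The range is therefore about 31% to 41% after allowing for simulation error. Independence gives the upper figure of 46%, which is not realistic for related markers measured repeatedly in the same patients.

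**3. Precision lost by leaving out baseline.** The variance of the adjusted arm difference relative to the unadjusted one is about 1 − r², where r is the correlation of baseline with follow-up (assumed). The equivalent gain in patients is 1/(1 − r²) − 1. Power is for an assumed true difference of 0.4 SD with 100 per arm; unadjusted it is 80.7%.

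| r | 1 − r² | Equivalent extra patients | Adjusted power |
|---|---|---|---|
| 0.3 | 0.91 | 10% | 84.3% |
| 0.5 | 0.75 | 33% | 90.4% |
| 0.7 | 0.51 | 96% | 97.7% |

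**4. Chance imbalance.** If the arms happen to differ by 0.2 SD at baseline, the unadjusted follow-up difference carries r × 0.2 SD: 0.5 × 0.2 = 0.10 SD, or 0.7 × 0.2 = 0.14 SD.

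**5. Reading paired tests side by side.** Suppose both arms have the same true change and each paired test has power p. The chance that exactly one arm is significant is 2p(1 − p): 42% at p = 0.3, 50% at p = 0.5 and 32% at p = 0.8. Such a pattern says little about a treatment effect.

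**The case against.** The strongest reply is that the plan already contains the right comparison. Patients are randomised 1:1, and the levels are to be "compared between the treatment group and the control group at each specific evaluation timepoint". With complete data that test is unbiased on average and has the correct error rate for each single test. This stands: the fault is lost precision and exposure to chance imbalance, not invalidity.

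Several stronger readings are tempting, but the protocol does not support them:
- **That within-arm change will be credited to the cells.** Section 12.3.4 nowhere says so, and it does not plan to compare significance across arms. Step 5 describes a risk in reporting, not a planned inference.
- **That improvement in both arms is to be expected from regression to the mean or newly started antivirals.** The entry criteria set no threshold on the four markers and do not say that anti-HBV therapy begins at entry.
- **That only t-tests are used, or that baseline is ignored throughout.** A non-parametric test is allowed, and the paired tests do use baseline. It is missing only from the between-arm tests.
- **That the tests run over every laboratory visit to week 48.** Blood is also drawn at weeks 2, 4 and 8, but section 7.2 sets evaluation at three visits, so 12 is the supported count.
- **That the sample-size rates show how many patients will have died by week 48.** Those rates concern disease-free survival at 60 months, and the primary analysis counts death or HCC. Patients living with HCC can still be sampled, and an early rate would need an assumed hazard shape.
- **That liver function alone carries the secondary conclusion.** Complications are also secondary, with their own between-arm tests and adjustment.

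One could also say that model choice belongs in a statistical analysis plan, which is not shown here. That would hold if the protocol were silent. It names the tests, so a better plan would have to depart from it.

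**Conclusion.** The point holds at moderate severity, as an inexpensive improvement to secondary analyses. Two facts come directly from the protocol: the paired tests estimate no treatment effect, and the 12 between-arm tests are unadjusted for baseline and have no multiplicity rule.

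The sizes depend on assumptions. The variance saved runs from 9% to 49% over r = 0.3 to 0.7. The false-positive range of about 31% to 41% rests on the assumed marker and visit correlations. The power figures also assume a 0.4 SD effect. No confirmatory claim rests on these endpoints, and the primary survival and HCC-free survival analyses are untouched.

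**What to change.** Replace the liver-function paragraph of section 12.3.4 with the following:
- For each marker, estimate the arm difference from a baseline-adjusted model: ANCOVA, or a mixed model for repeated measures with baseline as covariate. Use the screening measurement as baseline, and analyse TBIL on the log scale.
- Name week 48 as the key visit and report the arm difference with a 95% CI. Weeks 12 and 24 are supportive.
- Apply Holm to the four week-48 tests; the smallest p-value is judged against 0.05/4 = 0.0125. Without adjustment, four independent tests would give 1 − 0.95^4 = 18.5%.
- Present within-arm changes descriptively, without p-values.
- Add a sensitivity analysis on ranks with deaths ranked worst. It is needed because neither model solves the problem of values that do not exist after death; a mixed model in effect extrapolates them.

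The cost is a few lines of wording and standard SAS code. No new data, visits or patients are needed.
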